9.4.4 SAFETY ANALYSES

N/A

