2.3 RISK/BENEFIT ASSESSMENT

2.3.1 KNOWN POTENTIAL RISKS

- 1) Risk of boredom or fatigue (likely). Participants may become tired or bored during the intervention, assessments, and computerized cognitive testing.

To minimize risk: Participants will be allowed breaks in between testing sections and game-play is completed for no more than 25 minutes/day.

- 2) Loss of confidentiality around sensitive information (rare).

To minimize risk: All subjects are assigned research numbers, and all research information collected is linked to the subject only by this number. Great care is taken to remove all identifying information from research records. A single tracking file contains links to the research records and subject codes. Recruitment tracking files are kept only for the duration of recruitment. Any paper records are kept in locked file drawers in a locked room, to which only authorized research personnel have access. Any paper records with identifying information (consent form, payment records) are kept in locked file cabinets, physically separate from the research records. Computer records with identifying information are kept on secure, password protected servers. Staff members are trained to scrupulously protect the confidentiality of sensitive information, and take care to limit the printing of documents with identifying information and to avoid unnecessary discussion of subject names. Screening forms for subjects who do not qualify for the study will be destroyed, except for anonymous information unlinkable to the subjects (such as age, gender, and education).

However, if a subject may become eligible in the near future, e.g. they need to wait 1 month after a recent medication change, we will retain certain records so as not to repeat the assessments, with the assent of the potential participant.

- 3) Worsening of depressive symptoms, including suicidal thoughts plans, intentions or behaviors.

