2. After completing one half of the CCT training (2 weeks), participants will *earn* an additional \$25.
3. Once the full training has been completed (4 weeks of at least 80% compliance), participants will *earn* another \$25.
4. *After completing Assessment #2, participants will *earn* another \$25.
5. **For those who have completed Assessment #3 3-months post-intervention, participants earn an additional \$25.

Therefore, if all three assessments are completed in addition to the full EndeavorRx intervention, each participant will receive a total of \$150. All participants will have the opportunity to earn the same amount of compensation (if completed Assessment #3). Incentives are structured to promote retention of participants throughout the full intervention period, as well as for Assessment #3 (if applicable). Payment for all enrolled participants will be made in up to two payments: at payment step #4* and again at payment step #5**, if all activities completed. If participants screen out during Assessment 1, they will be provided payment after screening out. The participant will receive the incentive directly. If a participant withdraws from the study or does not complete certain parts of the study, payment will be distributed for the amount earned at the point of study discontinuation. If a participant does not complete at least 2 weeks of the CCT intervention, they will not complete the post-intervention assessments.

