6.4 STUDY INTERVENTION/EXPERIMENTAL MANIPULATION ADHERENCE

Tolerability and compliance with the intervention will also be assessed. The CCT application will measure the amount of time each day that the child spends playing the video game. Additionally, completion of self-report questionnaires and *Millisecond* assessments will be tracked to ensure that these assessments are completed within the specified time period. If the cognitive task battery and start of the cognitive training intervention are not completed within sufficient time of the baseline clinical and self-report assessment (i.e., within 14 days of completing the CDI; due to scheduling and/or equipment constraints), then the CDI and CDRS-R will be re-administered prior to initiating the cognitive task battery and cognitive training.

Assessments will include (refer to 1.3 Schedule of Activities for a list of which measures are completed at each assessment):

Assessments by Clinician

- a) C-SRSS
- b) CDRS-R
- c) K-SADS

Assessments Completed by Subjects

- a) MASC
- b) CDI
- c) SCARED (parent)
- d) CBCL (parent)
- e) ERQ-CA

Other Assessments

- a) ESS (parent and child)

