8.3.4 TIME PERIOD AND FREQUENCY FOR EVENT ASSESSMENT AND FOLLOW-UP

The occurrence of an adverse event (AE) or serious adverse event (SAE) may come to the attention of study personnel during study visits and interviews of a study participant presenting for medical care, or upon review by a study monitor.

All AEs, not otherwise precluded per the protocol, will be captured on the appropriate case report form (CRF). Information to be collected includes event description, time of onset, clinician's assessment of severity, relationship to study procedures (assessed only by those with the training and authority to make a decision), and time of resolution/stabilization of the event. All AEs occurring while on study will be documented appropriately regardless of relationship. All AEs will be followed to adequate resolution, such that the participant has been offered or received necessary care.

Any medical or psychiatric condition that is present at the time that the participant is screened will be considered as baseline and not reported as an AE. However, if the study participant's condition deteriorates at any time during the study, it will be recorded as an AE.

Changes in the severity of an AE will be documented to allow an assessment of the duration of the event at each level of severity to be performed. Documentation of onset and duration of each episode will be maintained for AEs characterized as intermittent.

A study team member will record events with start dates occurring any time after informed consent is obtained until 7 (for non-serious AEs) or 30 days (for SAEs) after the last day of study participation. At each study visit, the investigator will inquire about the occurrence of AE/SAEs since the last visit. Participants and/or their parent can spontaneously notify the investigator of an AE or health status change via phone call or email, if necessary, in between scheduled visits. Events will be followed for outcome information until resolution or stabilization.

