9.3 POPULATIONS FOR ANALYSES

Complete-Case Analysis Population: This population will consist of enrolled participants without missing data on variables of interest from Assessment #2.

Per-Protocol Analysis Dataset: This population will consist of participants who complete all four weeks of the intervention (with at least 80% compliance to the guidelines of 25 minutes/day for 5 days a week across the 4 weeks. Compliance of 80% can be achieved by completing at least 20 minutes of gameplay on 80% of the days that they could play the game in the 4 week period, if assuming a 5-day week. For instance, assuming that a participant would complete at least 20 minutes of gameplay for 20 days during the 4 week period, a participant with 80% compliance would engage in at least 20 minutes of gameplay for at least 16 days during this period. Compliance will be assessed using gameplay metrics provided by Akili that are automatically measured when the game is played on a participant's device.

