9.4 STATISTICAL ANALYSES

9.4.1 GENERAL APPROACH

Data will be analyzed using statistics software such as SPSS and R software. For descriptive statistics, means with standard deviation and range will be computed for continuous data (all behavioral data and some of the clinical data). In general, statistical significance is reported based on $p < 0.05$ two-tailed. Missing data from Assessment 3 (if applicable) will be handled using pairwise deletion. Missing data from Assessment 1 or 2 will be handled using listwise deletion.

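### No safety analysis and no all-treated set are planned, so adverse events and individual worsening have no summary and some treated children have no denominator

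*Combined protocol and SAP*

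**What the plan says.** Section 2.3.1 names this risk: "Worsening of depressive symptoms, including suicidal thoughts plans, intentions or behaviors". Section 8.3.4 states: "All AEs occurring while on study will be documented appropriately regardless of relationship". Collection runs from consent to 7 days (AEs) or 30 days (SAEs) after participation ends, and 8.3.3 grades severity, relatedness and expectedness. Section 8.2 lists the CDI as a safety assessment and defines worsening as a rise of more than 25% over baseline; 7.1 makes the same threshold a reason for discontinuation. Section 6.4 adds: "Tolerability and compliance with the intervention will also be assessed".

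In the statistical section, the entry under "9.4.4 SAFETY ANALYSES" is N/A. Section 9.3 defines two populations:

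- Complete-case: "This population will consist of enrolled participants without missing data on variables of interest from Assessment #2".
- Per-protocol: "This population will consist of participants who complete all four weeks of the intervention (with at least 80% compliance to the guidelines" on minutes and days of play).

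Section 9.4.1 adds: "Missing data from Assessment 1 or 2 will be handled using listwise deletion". Section 5.5 states: "If a participant does not complete at least 2 weeks of the CCT intervention, they will not complete the post-intervention assessments". Section 7.2 says that treated participants who withdraw or are discontinued are replaced.

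Two further provisions bear on safety. Section 9.4.6 plans an interim look, for participant safety, at average CDI at Time 2 and at the share withdrawing because of symptoms. Section 9.4.8 lists clinical and behavioral measures by timepoint.

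**The concern.** The safety data are specified with care as far as collection and grading, and then no analysis uses most of them. No section says how AEs, SAEs or individual CDI worsening will be summarised, or over which participants. The two defined populations depend on Assessment 2 data or on compliance, so neither is a treated set. A child who starts training and stops within the first 2 weeks can be in neither set and can be replaced. Such a child may well be one who had a tolerability or symptom problem.

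The trial is uncontrolled, section 10.1.6 plans no regular external monitor, and section 9.2 says the results should inform larger studies. Those studies will need the rates of worsening and of stopping for symptoms as well as effect sizes.

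**Working it through.** **1. What is collected, and what is summarised**

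- AEs and SAEs: collected and graded (8.3.3 to 8.3.5). No summary is planned: 9.4.4 is N/A, 9.4.6 does not use them and 9.4.8 does not name them.
- Individual CDI worsening: defined (8.2, 7.1), checked for each participant by the team (10.1.7), and visible in the CDI listing (9.4.8). No count or rate is planned.
- Stopping because of symptoms: reasons are recorded (7.1, 7.2), and 9.4.6 compares the number with a halting threshold. No reported rate is planned.
- Mean CDI change: planned (9.4.2, 9.4.6). A mean falls whenever the decreases add up to more than the increases, so it cannot show how many children worsened.

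**2. Where a treated child falls**

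- Four weeks at 80% compliance, Assessment 2 done: in both sets.
- Stops CCT after 2 weeks or more, Assessment 2 done: in the complete-case set.
- Compliant but Assessment 2 missed: meets the per-protocol wording, but listwise deletion removes the child from any pre-post comparison.
- Stops before 2 weeks: under 5.5 there is no Assessment 2, so not complete-case; four weeks were not completed, so not per-protocol. If the child also withdraws or is discontinued from the study, 7.2 adds a replacement. The plan does not say whether the replaced child stays in any count.

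For the last case, 7.1 reads differently: after stopping CCT the remaining procedures go ahead, and outcome assessments follow the schedule where possible. Sections 5.5 and 7.1 conflict and must be reconciled.

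**3. The plan's one safety number**

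Section 9.4.6 gives more than one third of participants as about 7.

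- N = 30: 30/3 = 10, so more than one third needs 11. Seven is 7/30 = 23.3%.
- N = 32: 32/3 = 10.7, so again 11. Seven is 7/32 = 21.9%.
- Seven exceeds one third at N = 20 (7/20 = 35%) and equals it at N = 21.

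The figure is not reproduced at the planned size. The fraction and the count must be reconciled.

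**4. What a safety table could show**

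Exact (Clopper-Pearson) 95% limits. With 0 events, upper = 1 − 0.025^(1/n). With x events, lower = the 0.025 quantile of Beta(x, n − x + 1) and upper = the 0.975 quantile of Beta(x + 1, n − x).

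- 0/30: upper limit 1 − 0.025^(1/30) = 11.6%.
- 3/30 = 10%: 2.1% to 26.5%.
- 6/30 = 20%: 7.7% to 38.6%.
- 9/30 = 30%: 14.7% to 49.4%.

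**5. Illustration (assumed; the documents give no event or dropout rates)**

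Suppose 3, 6 or 9 of 30 treated children lack Assessment 2 and none of the rest worsens. The children with data show 0/27, 0/24 or 0/21. The treated-group rate could then be anything from 0/30 up to 3/30, 6/30 or 9/30, that is, up to 10%, 20% or 30%.

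Assessment 3 is discontinued, so Assessment 2 holds the only CDI scheduled after training starts. The upper ends therefore require worsening that came to light by another route, such as the spontaneous report mentioned in 6.5.1.

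**The case against.** The strongest reply is that the plan does use safety data. Section 9.4.6 is a safety analysis in purpose and tracks symptom-related withdrawals. Section 9.4.8 lists each child's CDI. Section 10.1.7 has the team check every child for worsening. Section 7.1 keeps outcome assessments going after discontinuation where possible, and 8.2 makes a missed Assessment 2 CDI a reportable deviation. All of this stands, and it rules out several stronger readings:

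- A reader might infer that safety data never reach a result, or that the mean CDI change in completers is all that is left. Sections 9.4.6 and 9.4.8 contradict both. What is missing is a planned summary of AEs and SAEs, a count of individual worsening, and a denominator.
- A reader might infer that every early stopper is lost. A child who stops after 2 weeks and completes Assessment 2 stays in the complete-case set.
- A reader might take N/A as a deliberate decision not to analyse safety. The document also writes N/A under 8.3.6 and 9.4.5, although SAE handling and descriptive statistics appear elsewhere. For AE summaries, however, nothing appears elsewhere.
- A reader might take 0/27 against 3/30 as a bias in a planned summary. No section says AE counts would use the 9.3 sets, and the 3 is hypothetical.

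It is also fair that safety is not a stated objective in section 3, and that the tolerability sentence sits in the adherence section. Neither point supplies the missing summary. The interim rule covers no AEs, its average CDI can include only children with a Time 2 score, and a listing gives no rate.

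**Conclusion.** The point holds in a limited form. Section 9.4.4 plans no safety analysis, 9.3 defines no all-treated set, and no other section plans an AE or SAE summary or a count of children meeting the protocol's worsening definition. Under 5.5, children who stop before 2 weeks fall outside both populations, and 7.2 replaces those who leave the study. Followed as written, the plan yields a mean CDI comparison, a halting rule and listings, but no harm rates over everyone treated.

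The size of the effect on the safety picture is unknown. The ranges up to 10%, 20% and 30% rest on assumed numbers of children without Assessment 2 among 30 treated. The finding itself rests on the text and does not depend on those figures. It does not affect the primary efficacy test.

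**What to change.** Replace N/A in 9.4.4 with one paragraph and one table.

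- Safety set: all participants who start CCT, including those withdrawn, replaced or without Assessment 2. Because treated withdrawals are replaced, this denominator may exceed 30.
- Counts, percentages and exact 95% CIs for the main rates: any AE, any SAE, CDI worsening as the protocol defines it, and stopping because of symptoms.
- Counts of AEs by severity and relatedness; no intervals needed.
- Children without an Assessment 2 CDI shown in a separate row, neither counted as not worsened nor dropped.
- The table placed beside the mean CDI change.

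Reconcile 5.5 with 7.1 on assessments after stopping CCT, and the one-third rule in 9.4.6 with its count. Which reading is right is for the investigators to decide.

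The cost is small, since the data are already collected. The downside is that about 30 participants give wide intervals, so even a clean record supports only a modest safety statement.

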9.4.5 BASELINE DESCRIPTIVE STATISTICS

N/A

9.4.6 PLANNED INTERIM ANALYSES

At Time 2, after the completion of the CCT intervention, CDI scores will be evaluated across all participants. If scores are significantly worse at Time 2 than at Time 1 (a significantly higher average CDI score across participants), then the study may be halted. Similarly, if greater than one third of the participants (~7 subjects) withdraw from the study due to symptoms, then the study may be halted. If there is no change, or an improvement in CDI scores (lower CDI scores), then the study will continue as planned. This interim analysis will be conducted with the intention of maintaining safety of participants, rather than for assessing the efficacy of the intervention.

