9.2 SAMPLE SIZE DETERMINATION

Sample size was determined based on results from a power analysis and feasibility of participant recruitment. A sample size of 32 participants would yield 80% power for the planned analyses in the current study, but 30 participants is a more achievable initial target for recruitment. Though there is minimal data

to generate hypothesized effect sizes, the proposed study will allow for generations of effect sizes to be used in future, larger studies.

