9.4.2 ANALYSIS OF THE PRIMARY ENDPOINT(S)

We hypothesize that CCT will increase cognitive control capacity and reduce depressive symptoms. The hypothesis will be tested using paired samples (repeated measures) t -tests (pre vs. post) for each dependent variable (CDI score and Millisecond battery composite score). Both of these dependent variables are interval variables.

Standard deviations and effect sizes will be assessed for each of these analyses.

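### The mean-CDI safety trigger in 9.4.6 requires statistical significance, gives no action for a non-significant rise, and is weak at small look sizes

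*Combined protocol and SAP*

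**What the plan says.** Section 9.4.6 describes the look: "At Time 2, after the completion of the CCT intervention, CDI scores will be evaluated across all participants". It states that the purpose is participant safety and not efficacy. Two conditions may lead to a halt.

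- **Mean CDI:** "If scores are significantly worse at Time 2 than at Time 1 (a significantly higher average CDI score across participants".
- **Withdrawals:** "if greater than one third of the participants (~7 subjects) withdraw from the study due to symptoms, then the study may be halted". This one needs no significance test.

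The continuation branch reads: "If there is no change, or an improvement in CDI scores (lower CDI scores), then the study will continue as planned".

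Section 9.4.6 gives no significance level, sidedness or number of participants for the look. The only level in the document is the general rule in 9.4.1: "statistical significance is reported based on $p < 0.05$ two-tailed". The test is not named either. For the primary CDI comparison, 9.4.2 uses "paired samples (repeated measures) t -tests (pre vs. post").

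Other safeguards stand elsewhere. Section 7.1 discontinues an individual whose CDI rises more than 25% from baseline. Section 10.1.2 lists grounds for suspension, including a determination of unacceptable risk. Section 10.1.7 has the team check each participant for worsening after the assessment. Safety analyses (9.4.4) are marked as not applicable, and 10.1.6 plans no regular external monitor.

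**The concern.** A two-tailed 5% test keeps false alarms rare: if nothing has changed, it signals worsening in 2.5% of looks. That is a reasonable priority for an efficacy claim. At a safety look in a small single-arm study of minors, the more serious error is a missed signal, and a small sample makes it likely.

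The wording adds to this. The CDI result has a branch for significant worsening and a branch for no change or improvement. A mean that is higher, but not significantly so, falls between them. A team applying the rule could take non-significance as no change and continue, although the data may be quite compatible with harm. Section 9.4.6 is the only place where the plan sets a statistical rule for a group-level rise in CDI.

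**Working it through.** **Inputs from the plan.** Level 0.05 two-tailed (9.4.1, the general rule). Paired t-test (9.4.2, assumed to apply to the look). Recruitment target: "30 participants is a more achievable initial target for recruitment" (9.2). The look size is not stated. The figure of about 7 as one third implies 7 × 3 = 21, whereas one third of 30 is 10.

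**Inputs assumed.** The plan gives neither an SD of CDI change nor a harmful effect. The true mean worsening δ is therefore expressed in SDs of change and ranged from 0.3 to 0.6, with 0.5 as the central case. Here n is the number with both CDI scores.

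**The plan's own figure.** Section 9.2 says 32 participants give 80% power but states no effect size, so 32 cannot be reproduced from the plan's inputs. It is consistent with an effect of 0.5 SD: ((1.960 + 0.842)/0.5)² = 31.4, rounded up to 32. The exact t calculation needs 34 and gives 78.2% power at 32. This makes 0.5 a natural central case, but it remains an assumption.

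**Formulas.** The observed mean rise needed to trigger, in SDs of change, is t(0.975, n−1)/√n. At n=10 this is 2.262/3.162 = 0.715; at n=21 it is 2.086/4.583 = 0.455. The chance of triggering is P(T > t(0.975, n−1)), where T is noncentral t with n−1 degrees of freedom and noncentrality δ√n. At n=21 and δ=0.5 the noncentrality is 2.291 and the chance is 59%, so 41% are missed.

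| n | Observed rise needed | Missed, δ=0.3 | δ=0.4 | δ=0.5 | δ=0.6 |
|---|---|---|---|---|---|
| 10 | 0.715 | 87% | 80% | 71% | 60% |
| 15 | 0.554 | 81% | 70% | 56% | 42% |
| 21 | 0.455 | 74% | 59% | 41% | 26% |
| 30 | 0.373 | 64% | 44% | 25% | 11% |

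At δ=0.5 the trigger misses more than half the time only up to n=17 (51%); at n=18 it misses 48%.

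**If harm is defined on the baseline SD.** A worsening of 0.5 baseline SD with an assumed pre-post correlation of 0.7 gives δ = 0.5/√(2 × 0.3) = 0.645. The chance of triggering is then 45% at n=10, 64% at n=15 and 80% at n=21.

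**The withdrawal trigger.** At n=21, more than one third means at least 8. By the exact binomial, the chance of reaching 8 is 4%, 28% and 65% if the true symptom-withdrawal rate is 20%, 30% and 40%.

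**One-sided alternatives at δ=0.5.** Chance of triggering:

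| One-sided level | n=10 | n=21 |
|---|---|---|
| 0.05 | 43% | 71% |
| 0.10 | 59% | 83% |
| 0.20 | 76% | 92% |

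Under no change, the false-alarm rate equals the level chosen.

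**The case against.** A reader might infer that the study halts only on a significant mean worsening, continues in every other case, and so misses a moderate harm more often than not. The documents do not support any of the three parts.

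- **Halts only.** The withdrawal condition in 9.4.6 needs no test, and 7.1, 10.1.2 and 10.1.7 add individual and discretionary safeguards.
- **Continues otherwise.** Continuation is prescribed only for no change or improvement. What happens after a non-significant rise is unstated; that it would be treated as no change is one possible reading.
- **More often than not.** At 0.5 SD this fails from n=18 upwards, including the implied 21 and the target of 30. It depends on an effect size and a look size that the plan does not give.

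The safeguards also have real force. In an illustrative simulation (baseline CDI mean 10 and SD 4, SD of change 3 to 5, δ=0.5, every individual rise above 25% counted as a symptom withdrawal), one or other trigger fired in 57% to 82% of looks at n=10 and 69% to 90% at n=21. Those inputs are assumed, however, and the plan does not say that a 7.1 discontinuation counts as a symptom withdrawal under 9.4.6. With no mean change, the same combination fired in 14% to 36% of looks at n=10 and 6% to 29% at n=21.

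Two further objections stand. The 0.05 two-tailed level is carried over from a general rule and is not set in 9.4.6; at one-sided 0.05 the trigger would do better. And a one-sided confidence limit above zero is itself a one-sided significance test, so the remedy changes the direction and level of the trigger and not its kind.

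What these objections leave is a gap. The withdrawal rule counts withdrawals, 7.1 and 10.1.7 concern individuals, and 10.1.2 is discretionary. None states how a group-level rise in CDI is to be judged.

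**Conclusion.** The point holds as a specification gap with a measurable cost. The look is for safety, but its mean-CDI trigger needs significance at a level borrowed from the general rule, the look size is unstated, and a non-significant rise has no assigned action. Under the central assumption of 0.5 SD of change, the trigger alone misses between 71% (n=10) and 25% (n=30) of true worsenings, and 41% at the implied 21. A smaller harm is missed more often and a larger one less often, as the table shows.

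The percentages rest on a paired t-test, the two-tailed 5% level and the assumed effects, and they describe this one trigger and not the whole safety system. The missing branch and the missing look size rest on the text alone. The matter should be corrected, but it does not show that the study lacks safety oversight.

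**What to change.** Rewrite the paragraph in 9.4.6 as follows.

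1. State how many participants with both CDI scores make up the look.
2. Report the mean CDI change with its confidence interval.
3. Replace the two-tailed test by a one-sided test for worsening (equivalently, a one-sided lower confidence limit for the mean rise above zero). The sponsor and IRB set the level in advance from its operating characteristics at the stated look size; the levels tabulated above are illustrations.
4. State that crossing the limit prompts a review by the study team and IRB of whether to halt. Section 9.4.6 now describes no review step.
5. State that a non-significant rise is not treated as no change.
6. Reconcile the figure of about 7 as one third with the target of 30.

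The cost is one paragraph; no efficacy analysis changes. The downside is more false alarms: the rate under no change rises from 2.5% to whatever one-sided level is chosen. Each would lead to a review and not to an automatic halt, in keeping with the present wording that makes halting optional.
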